### 3.2.1.1.2 Response Criteria - AML

- **Complete Remission (CR)**
  - Peripheral Blood Counts -Neutrophil count  $1 \times 10^9/L$ .
  - Platelet count  $\geq 100 \times 10^9/L$ .
  - Reduced hemoglobin concentration or hematocrit has no bearing on remission status.
  - Leukemic blasts must not be present in the peripheral blood.
  - Cellularity of bone marrow biopsy must be  $> 20\%$  with maturation of all cell lines with  $< 5\%$  blasts.
  - Extramedullary leukemia, such as CNS or soft tissue involvement, must not be present.
- **Complete Response in the absence of total platelet recovery (CRp)**
  - Bone marrow ( $<5\%$  blasts) with adequate bone marrow cellularity, no evidence of circulating blasts or extramedullary disease and normalization of peripheral blood counts except for platelets (neutrophil count  $=1,000/\mu L$ ).
- **Partial Remission (PR)**
  - Requires that all of the criteria for complete remission be satisfied except that the bone marrow may contain  $> 5\%$  blasts but  $< 25\%$  blasts. A marrow with  $<5\%$  blasts that contain Auer rods will also be considered a PR
- **Progressive Disease (PD)**
  - An increase of at least 25% in the absolute number of leukemic cells in peripheral blood or bone marrow/aspirate, the development of extramedullary disease, or other evidence of increased tumor burden.
- **Relapse**
  - Relapse following complete remission is defined as: Reappearance of blasts in the blood.
  - Presence of 5% blasts, not attributable to another cause (e.g., bone marrow regeneration).
  - If there are no circulating blasts and the bone marrow contains 5% to 20% blasts, then a repeat bone marrow performed 1 week later documenting more than 5% blasts is necessary to meet the criteria for relapse.

Patients achieving a CR, CRp, or PR will be considered responders. Given the lag between first administration of azacitidine and clinical response, bone marrow examinations will be performed before entry into study, at 6 months, and then at least 6-month intervals afterwards. The biopsies will help

document response to treatment for both MDS and AML patients and to determine endpoints where necessary. Best response will be used for study endpoint.

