#### **3.2.1.1 Response Criteria**

##### **3.2.1.1 Response Criteria – MDS**

- **Complete Response:**
  - Bone marrow:
    - <5% myeloblasts with normal maturation of all cell lines
    - Persistent dysplasia will be noted
  - Peripheral blood
    - Hgb >11 g/dL
    - Platelets 100x10/L
    - Neutrophils 1.0x10/L
    - Blasts 0%
- **Marrow Complete Response**
  - Bone marrow:
    - 5% myeloblasts and decrease by \_ 50% over pretreatment†
    - Peripheral blood: if HI responses, they will be noted in addition to marrow CR
- **Partial remission**
  - All CR criteria if abnormal before treatment except:
  - Bone marrow blasts decreased by > 50% over pretreatment but still < 5%
  - Cellularity and morphology not relevant
- **Cytogenetic response**
  - **Complete**
    - Disappearance of the chromosomal abnormality without appearance of new ones
  - **Partial**
    - At least 50% reduction of the chromosomal abnormality
- **Hematologic Improvement** - Response criteria responses must last at least 8 weeks and are categorized by cell line impairment at time of diagnosis:
  - **Erythroid response** requires that pretreatment hemoglobin (Hgb) must be Less than 11 g/dL to qualify for response and post-treatment, either:
    - Hemoglobin increase by  $\geq$  1.5 g/dL
    - Relevant reduction of units of RBC transfusions by an absolute number of at least 4 RBC transfusions during 8 weeks compared with the pretreatment transfusion number in the previous 8 weeks. Only RBC transfusions given for a Hgb of  $\leq$  9.0 g/dL pretreatment will count in the RBC transfusion response evaluation
  - **Platelet response** requires pretreatment must be  $< 100 \times 10^9/L$  to qualify for response and post-treatment, either:
    - Absolute increase of  $\geq 30 \times 10^9/L$  for patients starting with  $> 20 \times 10^9/L$  platelets
    - Increase from  $< 20 \times 10^9/L$  to  $> 20 \times 10^9/L$  and by at least 100%
  - **Neutrophil response** requires pretreatment must be  $< 1.0 \times 10^9/L$  to qualify for response and at least 100% increase and an absolute increase  $> 0.5 \times 10^9/L$ .
- **Stable disease**
  - Failure to achieve at least PR, but no evidence of progression for 8 wks
- **Disease progression**
  - For patients with:

- Less than 5% blasts: 50% increase in blasts to 5% blasts
- 5%-10% blasts: 50% increase to 10% blasts
- 10%-20% blasts: 50% increase to 20% blasts
- 20%-30% blasts: 50% increase to 30% blasts
- Any of the following:

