## 4 Subject Selection and Withdrawal

### 4.1 Inclusion Criteria

1. Patients must have a diagnosis of one of the following:
  - MDS (Arm A)
    - i. High-risk MDS defined as: >5% blasts in bone marrow and/or the following cytogenetic categories: presence of inv(3)/t(3q)/del(3q), -7/del(7q), complex cytogenetics (3 or more abnormalities)
  - AML (Arm B)
    - i. Relapsed/refractory/unable to tolerate conventional chemotherapy
  - MDS or AML clinical diagnosis with prior therapy with azacitidine (Arm C)
- \*Note: As of July 2018, only high-risk MDS patients will be eligible as Arm B is closed. As of October 2017, those patients with MDS who have received prior treatment will now be enrolled on Arm A as Arm C is closed.
2. Patients must be  $\geq$  18 years old
3. Patients must have an ECOG performance status of  $\leq$  2 (see Attachment 1).
4. Patients must have a life expectancy of at least 4 weeks.
5. Patients must be able to consume oral medication.
6. Patients must have completed any radiotherapy four weeks prior to study entry, 0-2 weeks for local palliative XRT (small port).
7. Patients must have recovered from the toxic effects of any prior chemotherapy to < Grade 2 (except for alopecia).
8. Required initial laboratory values: Creatinine  $\leq$  2.0mg/dL; total or direct bilirubin  $\leq$  1.5mg/dL (if not due to the leukemia itself or known Gilbert's Syndrome); (as documented by treating physician) SGPT (ALT)  $\leq$  3xULN; glucose <200 mg/dL, negative pregnancy test for women of child-bearing potential.
9. Patients must be able to sign consent and be willing and able to comply with scheduled visits, treatment plan and laboratory testing.
10. Patients may have had a prior stem cell transplant (autologous or allogeneic), however they may not have active GvHD, nor be on any immunosuppression

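### The AML partial-remission rule requires no fall in marrow blasts from baseline, so a patient who enters with 5–25% blasts can be scored a responder with an unchanged marrow.

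*Combined protocol and SAP*

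**What the plan says.** Section 3.2.1.1.2 describes AML PR as follows: "Requires that all of the criteria for complete remission be satisfied except that the bone marrow may contain" blasts above 5% and below 25%. The complete-remission items that must still be met are the neutrophil and platelet thresholds, no circulating blasts ("Leukemic blasts must not be present in the peripheral blood"), marrow cellularity above 20% with maturation of all lines, and no extramedullary disease. The pretreatment marrow is not mentioned.

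The same section sets the endpoint: "Patients achieving a CR, CRp, or PR will be considered responders", and "Best response will be used for study endpoint". Progression is defined separately, as "An increase of at least 25% in the absolute number of leukemic cells in peripheral blood or bone marrow/aspirate", new extramedullary disease or other evidence of increased tumor burden. Relapse includes "Presence of 5% blasts, not attributable to another cause (e.g., bone marrow regeneration"). It also covers a marrow of 5% to 20% without circulating blasts, if a repeat marrow a week later is above 5%.

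The MDS criteria in section 3.2.1.1 do refer to baseline. MDS PR reads "Bone marrow blasts decreased by > 50% over pretreatment but still < 5"%, and marrow complete response also asks for a 50% decrease over pretreatment.

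For AML, section 4.1 admits patients to Arm B as "Relapsed/refractory/unable to tolerate conventional chemotherapy", with no minimum blast percentage. Arm C took MDS or AML after prior azacitidine. Section 7.1 records that Arm B closed after 27 patients and Arm C after 7.

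**The concern.** A response category should show change under treatment. Here the AML window overlaps the blast range at which the protocol itself declares relapse. A patient can enter inside the window, stay there, and be counted as a responder if the blood and remaining marrow items are met. A rising marrow can also fall inside the window.

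At stake is the primary endpoint for AML. The error runs one way: the missing requirement can add responders who did not improve, and it cannot remove any. The reported AML rate would then mix activity of the regimen with stable or worsening low-blast disease.

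**Working it through.** **1. Can an unchanged marrow score PR?** Setting the passages side by side:
- Entry: Arm B sets no blast minimum (4.1), and relapse is recognised from 5% marrow blasts, including without circulating blasts (3.2.1.1.2). Entry at 5–25% is possible.
- Scoring: a later marrow above 5% and below 25% meets PR if neutrophils, platelets, circulating blasts, cellularity with maturation, and extramedullary status all qualify. A patient may meet these items at entry, or reach them by count recovery alone.
- Example: 10% → 10% is a 0% change and scores PR if those items are met.

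**2. Can the same marrow also meet progression?** Progression refers to the absolute number of leukemic cells, so blast percentage is used here as a proxy at constant cellularity.
- 8% → 20%: (20 − 8)/8 = +150%, inside the PR window.
- 18% → 24%: (24 − 18)/18 = +33%, inside the PR window.
- 20% → 24.9%: (24.9 − 20)/20 = +24.5%, below the 25% rise.
- Limit: 25%/1.25 = 20%. PR and progression can coincide only from baselines below about 20%, and only through the marrow part of the progression rule. Circulating blasts or extramedullary disease already exclude PR.

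**3. Reproducing the Arm B design (7.1).** Stop if 3 or fewer of 13 respond; reject if 12 or fewer of 43 respond; null rate 0.20, alternative 0.40.
- P(stop early) = P(X₁ ≤ 3 | 13, p)
- P(declare active) = Σ over x = 4 to 13 of P(X₁ = x | 13, p) × P(X₂ ≥ 13 − x | 30, p)
- At p = 0.20: early stop 0.7473; expected size 13 + (1 − 0.7473) × 30 = 20.58; false-positive rate 0.0496. At p = 0.40: power 0.8002. The printed 0.747, 20.58, 0.050 and 0.200 (type II error) are all reproduced.

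**4. Illustration of sensitivity.** Assume a fraction f is scored PR without improvement and the rest respond at the null 20%. The apparent rate is 0.20 + 0.80f. The documents do not give f.

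| f (assumed) | Apparent rate | Early stop | False-positive rate |
|---|---|---|---|
| 0% | 0.200 | 0.747 | 0.050 |
| 2% | 0.216 | 0.697 | 0.082 |
| 5% | 0.240 | 0.618 | 0.150 |
| 10% | 0.280 | 0.485 | 0.313 |

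Here f counts patients actually scored PR. If it is read instead as the fraction meeting PR at entry, and only half still meet it at a post-treatment marrow (a further assumption), the effective fraction halves. Then 5% gives an apparent rate of 0.220 and a false-positive rate of 0.091, and 10% gives 0.240 and 0.150.

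**The case against.** The strongest reply is that the affected group is narrow and the arm is closed. PR demands every other complete-remission item, so a patient scored PR with no change at all needs adequate neutrophils and platelets, a maturing marrow with cellularity above 20%, no circulating blasts and no extramedullary disease. Section 3.2.2.1 expects these patients to need frequent transfusions. Meeting the limits at entry is also not yet a scored response: they must be met at a post-treatment marrow, with the first scheduled one at 6 months, although earlier marrows are allowed. All of this stands and makes the group smaller. It does not close the gap, because eligibility does not exclude such patients and count recovery with an unchanged marrow is enough.

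Some stronger readings are tempting, but the documents do not support them.
- A reader might infer that, because best response is used, PR prevails over progression on the same marrow. Best response ranks assessments over time; the text is silent on which label applies when one marrow fits both.
- A reader might insert two such patients among the 27 accrued: 0.20 + 0.80 × 2/27 = 0.259, which gives 0.22 under the 43-patient rule. That rule was not completed. The printed limit of more than 12 responders, applied at 27 patients, gives 0.011, and no new cutoff is stated.
- A reader might cite the 20–30% blast group in section 1.1 as evidence about Arm B. It describes a cited study's population, and PR together with progression is not possible from 20% upward on the percentage scale.
- A reader might expect a false-positive decision in Arm C. It closed at 7 patients, short of its 10-patient first stage, so no decision under its printed rule is affected.

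**Conclusion.** The gap in the definition is real and can be read directly from the text: AML PR can be scored with no fall in marrow blasts. From baselines below about 20%, the same marrow may also meet progression, with no rule on which call prevails. The bias in the AML response rate can only be upward. Its size cannot be estimated, because the documents do not say how many AML patients entered inside the PR window or met its other conditions.

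The tabulated rates show how sensitive the printed 43-patient design is to a few such patients. They rest on assumed values of f and are not an estimate for this trial. What remains exposed is the response rate reported for the 27 Arm B patients and for any AML patients in Arm C. Since July 2018 only MDS patients can enrol, and their criteria do refer to baseline. This should be fixed, but it does not by itself invalidate the design.

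**What to change.** In section 3.2.1.1.2, add to AML PR a decrease of at least 50% in marrow blast percentage from the pretreatment marrow, and state that a marrow meeting the progression definition cannot be scored PR.

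Because Arm B is closed and open-label, this should not silently replace the primary endpoint. Apply it as a labelled re-score of the 27 Arm B patients and any AML patients in Arm C, using existing marrow reports. Report it beside the protocol-defined rate, with CR and CRp shown separately from PR, and give the number of patients who already met the PR limits at entry.

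Patients with at least 5000/µl circulating blasts at baseline may have no repeat marrow (Attachment 2, footnote 8). They could not have met PR at entry, so they need not be restricted to CR or CRp; use their diagnostic marrow as the baseline.

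The cost is the added wording and a review of reports already held, with no new procedure. The re-scored AML response rate may be slightly lower, and two rates have to be presented and explained.

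### The AML response criteria leave a marrow of exactly 5% blasts in no responder category, so a patient at 5% is not counted while an otherwise identical patient at 24% is

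*Combined protocol and SAP*

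**What the plan says.** All the relevant rules are in section 3.2.1.1.2, Response Criteria - AML.

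- **CR:** the marrow must show "maturation of all cell lines with $< 5\%$ blasts", together with count recovery, no circulating blasts, adequate cellularity and no extramedullary disease.
- **CRp:** "Bone marrow ( $<5\%$ blasts) with adequate bone marrow cellularity", with platelets the only count allowed not to recover.
- **PR:** "Requires that all of the criteria for complete remission be satisfied except that the bone marrow may contain" more blasts than CR allows; the window is that "the bone marrow may contain $> 5\%$ blasts but $< 25\%$ blasts".
- **Second route to PR:** a marrow below 5% with "blasts that contain Auer rods will also be considered a PR".
- **Responder rule:** "Patients achieving a CR, CRp, or PR will be considered responders".
- **Timing:** "Best response will be used for study endpoint". Marrows are scheduled before entry, at 6 months and at least every 6 months after that. Attachment 2, note 9, allows more frequent examinations at the investigator's discretion.

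The relapse definition in the same section also mentions 5%, but it applies after a CR: "Presence of 5% blasts, not attributable to another cause (e.g., bone marrow regeneration"). It adds that, without circulating blasts, a marrow of 5% to 20% must be repeated a week later and must then exceed 5%.

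Section 7.1 gives the Arm B design: 3 or fewer of 13 stops the arm, and 12 or fewer of 43 rejects the drug. It reports Arm B closed at 27 patients and Arm C at 7.

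**The concern.** The CR limit and the lower PR bound are both strict at 5%, so the two categories do not meet. Response should not get worse as the marrow gets better, yet as written it does at one point: 5.1% and 24% are responses, 4.9% is a response, and 5% is not. No clinical reason is given for this, and it is hard to imagine one.

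The rule defines the primary endpoint for Arm B and for any AML patients in Arm C. Applied literally, it can only lower the response rate. If it is left as it is, a marrow at 5% would have to be adjudicated case by case in an open-label, single-regimen study, and the text gives no guidance.

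**Working it through.** **1. The rule applied literally.** Assume every other CR criterion is met.

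| Marrow blasts | No Auer rods | Auer rods | Responder? |
|---|---|---|---|
| 4%, 4.9% | CR | PR | yes |
| 5% | none | none | no |
| 5.1%, 6%, 24% | PR | PR | yes |
| 25% | none | none | no |

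The Auer-rod route does not rescue 5%, because it also requires fewer than 5% blasts. The exclusion at 25% is the intended upper limit; the one at 5% is a gap.

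**2. The plan's own design figures.** Inputs from section 7.1 for Arm B: r1/n1 = 3/13, r/n = 12/43, p0 = 0.20, p1 = 0.40. With X1 the stage 1 responders among 13 and X2 the responders among the further 30:

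- PET = P(X1 <= 3 | p0) = 0.7473 (stated 0.747).
- E[N] = 13 + (1 - 0.7473) x 30 = 20.58 (stated 20.58).
- P(X1 >= 4 and X1 + X2 >= 13) = 0.0496 at p0 (stated 0.050) and 0.8002 at p1 (stated type II error 0.200).

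The design calculation is correct. The issue lies only in what is counted as a response.

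**3. Possible size.** The documents give no frequency for a marrow at exactly 5%, so this step rests on assumptions:

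- Section 1.1 cites a retrospective azacitidine AML series with 10 PRs among 82 patients (12%). Take 10/82 as the share of patients in the 5% to <25% window. The PR definition used in that series is not given.
- Assume the reportable values in the window are equally likely. Then 5% is 1 of k values, where k depends on how finely blasts are reported.

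Loss in response rate = (10/82)/k. Arm B power is recomputed at 0.40 minus that loss. Expected patients affected = 27 x loss.

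| Reporting of blasts | k | Loss (points) | Arm B power | Expected patients of 27 |
|---|---|---|---|---|
| 500-cell count (0.2% steps) | 100 | 0.12 | 0.797 | 0.03 |
| 200-cell count (0.5% steps) | 40 | 0.30 | 0.792 | 0.08 |
| Whole percents | 20 | 0.61 | 0.784 | 0.16 |
| Only 5, 10, 15, 20 | 4 | 3.05 | 0.71 | 0.82 |

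**4. Effect of a single patient.** 1/27 = 3.7 points of the observed Arm B rate.

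**The case against.** **The signs may be a reading artefact.** Comparison signs in this section are damaged in the text available: the CR neutrophil count has none, and the relapse line may have lost one. A one-symbol point must be checked against the source PDF. However, the signs that create the gap (<5%, >5%, <25%) are all present and legible. This stands as a condition, not a rebuttal.

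**The relapse text does not settle which bound is wrong.** A reader might infer that, because relapse refers to 5% blasts, the protocol places 5% outside remission and the PR bound must be the error. The text does not support that inference. The repeat-marrow clause requires more than 5%, which is the same strict bound as PR, and the relapse definition applies only after a CR. The gap is real, but the relapse wording alone does not dictate how to close it.

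**The effect is probably small and partly mitigated.** Best response is used and marrows are repeated, so one reading of 5% need not be final. The bias is downward, so it cannot create a false positive. Non-responder status is also an inference: the protocol never says how an unclassified patient is scored, only that responders are CR, CRp and PR. All of this stands, and it limits the size. It does not help a patient whose best marrow is 5%.

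**The correction is post hoc.** It changes a primary-endpoint definition in closed, open-label arms and can only add responders. That is a fair warning, and it determines how the correction should be made and reported.

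**Conclusion.** The gap is established from the text alone, subject to the PDF check: between otherwise identical patients meeting all other CR criteria, 24% counts as a response and 5% does not.

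Its numerical effect is unknown and probably small: 0.1 to 0.6 points of response rate, with Arm B design power of 0.797 to 0.784 against 0.800. These figures rest on the 10/82 share and on equally likely reported values, neither of which the documents establish for this trial.

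Two stronger readings are tempting but unsupported. The first is that power falls to 0.71; that requires every marrow report to be rounded to a multiple of 5, for which the documents offer nothing. The second is that one patient could change a stage decision. Arm B closed at 27, past its first stage of 13 and short of 43, and Arm C closed at 7, before its first stage of 10. Only MDS patients are now eligible (section 4.1), so no AML stage decision remains open, and the power figures describe the design rather than a test still to be run.

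What remains at stake is how the enrolled AML patients are classified and reported. The expected number affected in Arm B is 0.03 to 0.8 patients, each worth 3.7 points.

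**What to change.** 1. Check the comparison signs in section 3.2.1.1.2 against the source PDF.
2. If they read as above, change the AML PR window to >=5% and <25%. CR and PR then meet with no gap and CR is not loosened. Placing 5% in CR would also close the gap, but it would relax the stricter category.
3. Apply the corrected rule uniformly to all AML patients in Arms B and C, and record it as a correction of the definition made without regard to its effect on the result.
4. If any patient is reclassified, report the response rate under the current wording alongside the corrected one, because the change can only add responders.

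The cost is one symbol, a short amendment note and a check of marrow values already recorded. No new data are needed, and the sample size and decision rules do not change.

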### 3.2.2 Secondary Endpoints

#### 3.2.2.1 Safety and tolerability

- The combination of these drugs will be deemed safe if the number of adverse events is no more than 10% greater than the additive number of events of azacitidine and sirolimus if administrated separately. This will be based upon data in the original phase 2 trials of azacitidine demonstrating an 8% toxic death rate and therefore be 18% of the total number enrolled (approx.  $40 \times 18\% = 7$ ).
- Toxicity will be graded according to the NIH CTC version 4.0 (<http://ctep.cancer.gov/reporting/ctc.html>). Toxicity refers to toxic events during the full course of treatment (through day 21) that are attributed as possibly, probably or definitely due to treatment.

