## Study Summary

Title	A Phase II Study of Azacitidine and Sirolimus for the Treatment of High-risk MDS and Patients with Acute Myeloid Leukemia Refractory To or Not Eligible for Intensive Chemotherapy.
Short Title	Sirolimus/Azacitidine
Phase	II
Methodology	Open label
Accrual Duration	83 months
Study Center(s)	1. Jefferson Health Network (Center City Hospital, Abington Hospital, Aria Hospital, Methodist Hospital and NJ Division (Kennedy) Hospital
Objectives	This is a study to determine estimate of efficacy of sirolimus when administered with azacitidine.  Secondary objectives are to determine the pharmacodynamic effect of rapamycin on inhibition of mTOR and the safety of the combination of the regimen.
Number of Subjects	74;
Diagnosis and Main Inclusion Criteria	

Adults with high-risk MDS or relapsed or refractory AML or those unable or unwilling to tolerate high dose chemotherapy.

Age <math>\geq 18</math>

Study Product, Dose, Route, Regimen	Sirolimus loading dose of 12mg on day 1 followed by a single daily dose of 4 mg/ day on days 2 through 10 or 12  Azacitidine 75 mg/m  /d for 5 consecutive days, two days rest, then two consecutive days every 28 days or: Azacitidine 75 mg/m  /d for 7 consecutive days. After 2 cycles, may increase dose to 100 mg/m 
Duration of administration	Until disease progression or toxicity requiring discontinuation of the drug
Reference therapy	Fenaux et al. J ClinOncol. 2010 Feb 1;28(4):562-9.
Statistical Methodology	This study is a phase II trial. The study will be stratified to arms A, B, and C. Arm A (high risk MDS) will need 40 patients total for an optimal Simon 2-stage design (with alpha=0.1 and 80% power) with 23% standard response rate vs. an expected 40% response rate. Arm B (AML) We will need 43 patients total for an optimal Simon 2-stage design (with alpha=0.05 and 80% power) with 20% standard response rate vs. an expected 40% response rate. Arm C (either MDS or AML with prior Azacitidine therapy) will need 29 patients total for an optimal Simon 2 stage design (with alpha = 0.05 and 80% power) with a 5% response rate versus a 20% response rate.

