### EXPERIMENTAL DESIGN SCHEMA:

DAY:	1*	2	3	4	5	6	7	8	9	10	11	12
Sirolimus:	12mg	4mg	4mg	4mg	4mg	4mg	4mg	4mg	4mg	4mg	4mg	4mg
Azacitidine:				X	X	X	X	X			X	X
Azacitidine-Alt:				X	X	X	X	X	X	X		
PD:	X 			X 								
PK:				X 								

PD-Sample drawn before sirolimus dosing.

PD- Sample drawn before azacitidine administration

PK- Sample drawn before sirolimus and azacitidine administration

\*The dose of azacitidine used in this trial is the FDA approved dose, stemming from multiple phase II-III trials.

This dose of sirolimus was discovered to be the MTD in the Phase 1 trial evaluating sirolimus in addition to MEC chemotherapy for relapsed/refractory AML. It was also utilized in a pilot trial for AML patients, a pilot trial in ALL patients, and a larger phase II AML trial conducted at our institution and/or the University

of Pennsylvania.

Prospective subjects will be informed of all anticipated and possible unanticipated adverse effects of drug treatments. All of the drugs studied in this proposal have been used widely in humans at the doses described. Anticipated treatment-related adverse events include myelosuppression, febrile neutropenia and fatigue. Alternative therapies, including standard chemotherapy, investigational agents, and supportive care-only, will be discussed with potential subjects prior to informed consent. Prospective subjects will also be advised of issues related to confidentiality in accordance with HIPAA guidelines. Because sirolimus is an immunosuppressant, the infectious toxicity of this regimen may be increased compared to azacitidine alone.

A total of 6 infectious deaths have occurred in the more than 80 subjects treated on both sirolimus-MEC studies (7.5%) including 4/62 (6%) at the doses planned for this trial. This rate of toxic deaths does not differ from published data, but this important safety signal will be monitored closely. A stopping rule with respect to safety is included in our design and consideration for early termination will be made in consultation with the medical monitor and biostatistician if excess toxicity is suspected.

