## 7 Statistical Plan

### 7.1 Sample Size and Study Duration

This study is considered a phase II study.

For the MDS Arm A:

The optimal two-stage design to test the null hypothesis that  $P \leq 0.230$  versus the alternative that  $P \geq 0.400$  has an expected sample size of 24.60 and a probability of early termination of 0.592. If the drug is actually not effective, there is a 0.090 probability of concluding that it is (the target for this value was 0.100). If the drug is actually effective, there is a 0.200 probability of concluding that it is not (the target for this value was 0.200). After testing the drug on 14 patients in the first stage, the trial will be terminated if 3 or fewer respond. If the trial goes on to the second stage, a total of **40 patients** will be studied. If the total number responding is less than or equal to 12, the drug is rejected.

For the AML Arm B:

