**Note: As of July 2018, Arm B was closed after accruing 27 patients.**

The optimal two-stage design to test the null hypothesis that  $P \leq 0.200$  versus the alternative that  $P \geq 0.400$  has an expected sample size of 20.58 and a probability of early termination of 0.747. If the drug is actually not effective, there is a 0.050 probability of concluding that it is (the target for this value was 0.050). If the drug is actually effective, there is a 0.200 probability of concluding that it is not (the target for this value was 0.200). After testing the drug on 13 patients in the first stage, the trial will be terminated if 3 or fewer respond. If the trial goes on to the second stage, a total of **43 patients** will be studied. If the total number responding is less than or equal to 12, the drug is rejected.

For the pre treated Arm C:

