**Note: As of October 2017, Arm C was closed after accruing 7 patients.**

The optimal two stage design to test the null hypothesis that  $P \leq 0.05$  versus the alternative that  $\geq 0.200$  has an expected samples size of 10 and a probability of early termination of 0.508. If the drug is actually not effective, there is a 0.050 probability of concluding that it is (the target for this value was 0.050). If the drug is actually effective, there is a 0.200 probability of concluding that it is not (the target of this value was 0.200). After testing the drug on 10 patients in the first stage, the trial will be terminated if zero patients respond. If the trial goes on the second stage, a total of **29 patients** will be studied. If the total number responding is less than or equal to 3, the drug is rejected.

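### Section 3.2.2.1 turns a raw toxic-death count into a safety verdict with no confidence bound or stated error rate, on an unsettled denominator

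*Combined protocol and SAP*

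**What the plan says.** Safety and tolerability is a secondary objective (section 2.2). Section 3.2.2.1 gives the decision criterion: "The combination of these drugs will be deemed safe if the number of adverse events is no more than 10% greater than" the additive number for azacitidine and sirolimus separately. It then calibrates the criterion on earlier azacitidine trials "demonstrating an 8% toxic death rate and therefore be 18% of the total number enrolled", and works the limit as about 40 times 18%, giving 7.

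The 40 matches the full size of Arm A in section 7.1: "If the trial goes on to the second stage, a total of 40 patients will be studied". The Study Summary gives a larger total, "Number of Subjects 74". That total equals Arm A plus the two closed arms in section 7.1: "As of July 2018, Arm B was closed after accruing 27 patients" and "As of October 2017, Arm C was closed after accruing 7 patients".

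Section 3.2.2.1 counts toxicity through day 21. Section 8.1 runs adverse event reporting to 30 days after the last administration of study treatment.

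Section 1.6 says "A stopping rule with respect to safety is included in our design". Section 8.4 consists only of a reference to section 7.2. Section 7.2 covers Kaplan-Meier estimation, baseline summaries and the S6 analyses, and has no toxicity analysis or boundary.

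**The concern.** The cut-off of 7 is the expected count at the 18% limit, rounded down, and the observed count is compared with it directly. A point estimate therefore becomes a verdict with no allowance for sampling error. The response endpoints carry stated alpha and power in section 7.1; the safety verdict carries neither.

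This matters because section 1.6 warns that sirolimus, as an immunosuppressant, may add infectious toxicity. It cites 4/62 infectious deaths at the planned doses in the earlier sirolimus-MEC studies and treats this as a signal to watch closely. As written, the trial could report the combination as safe after 7 toxic deaths in 40 patients, and a reader would not learn how high a true rate that result leaves open.

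**Working it through.** **Inputs.** Reference rate 8%, margin 10 percentage points, limit 18%, n = 40, cut-off 7 (all section 3.2.2.1). Total 74 (Study Summary). Arm sizes 40, 27 and 7 (section 7.1). The documents give no confidence level, so 95% and 90% one-sided are shown as assumptions.

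**Reproducing the plan's figure.** 8% + 10% = 18%; 40 × 0.18 = 7.2, rounded down to 7. The plan's figure is reproduced. The wording is inclusive, so 7 passes.

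**How the rule behaves.** P(pass) = P(X ≤ 7), X ~ Binomial(40, p):

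| True toxic-death rate | P(pass), ≤7/40 |
|---|---|
| 8% | 0.987 |
| 12% | 0.900 |
| 18% | 0.566 |
| 20% | 0.437 |
| 24% | 0.222 |
| 30% | 0.055 |

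**What a passing result leaves open.** At 7/40 = 17.5%, the exact (Clopper-Pearson) one-sided upper bound is 30.4% at 95% and 27.7% at 90%.

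**Denominator.** 40 + 27 + 7 = 74, the stated total. Applying 18% to 74: 74 × 0.18 = 13.3, so ≤13. P(X ≤ 13 | 74, p) = 0.535 at 18% and 0.362 at 20%. If the printed count of 7 were kept for 74 patients, P(pass) at 18% would be 0.032, but 7/74 is 9.5%, not 18%. The choice of denominator therefore changes the rule materially.

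**What a bound-based rule would do.** Require the exact one-sided upper bound to lie below 18%, n = 74:

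| Level (assumed) | Cut-off | Bound at cut-off | P(pass) at 8% | at 12% | at 18% |
|---|---|---|---|---|---|
| 90% | ≤8/74 | 17.0% | 0.864 | 0.46 | 0.066 |
| 95% | ≤7/74 | 17.0% | 0.761 | 0.32 | 0.032 |

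At the 90% level, 9/74 gives a bound of 18.5%, so 8 is the largest passing count.

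**The case against.** A reader might infer that a regimen at an unacceptable toxic-death rate is wrongly called safe more than half the time. The documents do not support that. The rule says no more than, so 18% is the inclusive edge of what the sponsor accepts, and passing there is not a misclassification under the rule as written. Any rule that sets an observed rate against a threshold passes about half the time at that threshold. The figure also depends on the reading: 0.566 for ≤7/40 and 0.535 for ≤13/74, but 0.403 if 7 itself failed (against the inclusive wording) and 0.032 if the count of 7 were applied to 74. The text names adverse events and only the calibration uses deaths. Its 10% could also be read as relative (8% × 1.1 = 8.8%).

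Nor can it be said that the rule fails to discriminate. It passes 0.987 of the time at 8% and 0.055 at 30%; the weakness lies just above the limit.

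It would also go too far to say that a confidence-bound rule is required. At a true 12%, inside the sponsor's range, P(pass) falls from 0.90 under the present rule to 0.46 with the 90% bound on 74 patients. Requiring proof that the rate is below 18% is a design choice for a secondary endpoint in a single-regimen phase II trial. Sections 8.3.2 and 8.3.4 also provide expedited reporting of deaths and monitoring committee oversight.

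These points limit the criticism but do not remove it. Committee review sets no statistical boundary, and the plan still issues a verdict from a count without saying how often that verdict would be given at true rates above its own limit.

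**Conclusion.** The concern holds in limited form. Section 3.2.2.1 is the only numerical safety criterion in the documents, and it gives a safety verdict from a raw count with no bound or error rate. On its own worked figures the verdict would be given 44% of the time at a true 20% and 22% of the time at 24%, three times the 8% reference. A result at the cut-off leaves open a rate of about 30% (one-sided 95%).

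These sizes rest on the toxic-death event, a percentage-point margin and n = 40, which is the sponsor's own calculation. With 18% applied to all 74, P(pass) at 20% is 0.36. The event, denominator and window are unresolved in the text, so every figure is conditional on that reading. The point bears on what the trial may conclude about safety; it does not touch the primary response analysis.

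**What to change.** In sections 3.2.2.1 and 7.2:

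- Remove the safety verdict based on the count alone. Report the treatment-related death rate among all treated patients (planned 74), overall and by arm, with an exact confidence interval read against the sponsor's 18%.
- Reconcile the denominator (40 or 74), the event (adverse events or toxic death) and the window (day 21 in 3.2.2.1, or 30 days after the last dose in 8.1).
- State the operating characteristics of any count rule that is kept.

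If the sponsor wants a formal verdict, requiring the exact one-sided upper bound to lie below 18% is one option. The level must be declared as an assumption, with the pass probabilities tabulated above printed beside it.

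Cost: edits to two sections, with no extra patients. The safety statement becomes less favourable. Pooling combines MDS and AML, and 27 + 7 = 34 patients had already accrued in the closed arms when those arms closed, so outcomes may have been known. The change should therefore be dated and the by-arm rates shown.
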